CLINICAL STUDY PROTOCOLInterventional Drug or Biologic

A Pilot Study on the Safety and Efficacy of Mavoglurant in Alcohol Drinking

Protocol Number

2000021703

Protocol Version 2.9

PRINCIPAL INVESTIGATOR:

Name: [name]

Department: Yale School of Medicine Dept of Psychiatry

[contact]

Email Address: [contact]

IND Number: #137044

IND Holder: [name] NCT Number: NCT03327792

Study Phase 1:

Confidentiality Statement: This document is a confidential communication of the study sponsor ([name], Yale University School of Medicine). Acceptance of this document constitutes agreement by the recipient that no unpublished information contained herein will be published or disclosed without the sponsor's prior written approval, except that this document may be disclosed to appropriate Institutional Review Boards under the condition that they are requested to keep it confidential.

REVISION HISTORY:

Revision #	Version Date
2.0	1/11/2021
2.1	7/9/2021
2.2	12/16/2021
2.3	3/28/2022
2.4	6/6/2022
2.5	8/1/2022
2.6	9/12/2022
2.7	3/07/23
2.8 2.9	6/15/23 10/26/23

1 Synopsis

Primary Objective

The purpose of this study is to evaluate interactions between a moderate dose of alcohol and a non-competitive antagonist of the metabotropic glutamate receptor subtype 5 (mGLUR5), mavoglurant, on pharmacokinetic, physiological or behavioral responses in healthy social drinkers.

Study Duration

6 years, plus 1 year for data analysis

Study Design

This pilot study will examine interactions between alcohol and mavoglurant and explore the effects of mavoglurant on alcohol responses. This is a between subjects, double-blind design. We propose to recruit 40 male and female healthy volunteers (to achieve a completer sample of 28 participants) who meet criteria for social drinking (i.e., consuming 1- 6 standard alcoholic drinks per week and having engaged in at least one and no more than 12 binge drinking episodes in the past year), do not meet criteria for a DSM-V Alcohol Use Disorder, and who are willing to abstain from alcohol during the outpatient study medication treatment phase.

The study will consist of five parts: 1) Eligibility: Informed consent is obtained, and eligibility is evaluated, 2) Lab Session 1: Eligible subjects will then be exposed to a fixed dose of alcohol and monitor responses; we will randomize them to study medication (mavoglurant or placebo), 3) Outpatient Medication: Subjects will come in on a daily basis (or via zoom) for 7-10 days, when they will be observed when they take the study medication, and adverse events will be monitored, 4) Lab Session 2: Subjects will again be exposed to the same fixed alcohol dose at the first lab session, the following morning they will go in for a blood/urine collection 5) Follow Up Interviews: We will follow up with participants via phone, for two days after discharge and in-person, one week after discharge to assess for any potential remaining adverse events.

Number of Study Sites

This is a single site study

Study Population

40 social drinkers who are not currently seeking treatment for their drinking behavior, and who are willing to abstain from drinking alcohol during the study, and who are between 21-50 years of age.

Number of Participants

40 social drinkers will be recruited to achieve 28 completers.

Primary Outcome Variables

To evaluate the effect of mavoglurant on blood chemistries, urine toxicology and physiological safety measures before and after alcohol administration.

Secondary and Exploratory Outcome Variables (if applicable)

To evaluate the interactions of alcohol and mavoglurant on blood alcohol levels and mavoglurant levels.

APPROVED BY THE YALE UNIVERSITY IRB 11/22/2023

2000021703 Version 2.9

To explore the effects of mavoglurant on alcohol responses, including stimulation, sedation, intoxication, and cognitive/motor performance.

2 Abbreviations

Abbreviation	Explanation				
ADP	Alcohol Drinking Paradigm				
HRU	Hospital Research Unit				
СМНС	Connecticut Mental Health Center				
AUD	Alcohol Use Disorder				
CTNA	Center for Translational Neuroscience on Alcoholism				
AE	adverse event				
ALT	alanine aminotransferase				
AST	aspartate aminotransferase				
BAC	blood alcohol concentration				
CLIA	Clinical Laboratory Improvement Act				
CIWA-AR	Clinical Institute Withdrawal Assessment for Alcohol-revised				
DSM-5	Diagnostic and Statistical Manual of Mental Disorders – Fifth Edition				
DSMB	Data and Safety Monitoring Board				
EKG/ECG	electrocardiogram				
EtOH	ethanol				
FDA	Food and Drug Administration				
GGT	gamma-glutamyl transferase				

4.1 Introductory Statement

This document is a protocol for a human research study. The purpose of this protocol is to ensure that this study is to be conducted according to ICH GCP guidelines, and according to CFR 21 Part 312, other applicable government regulations and Institutional research policies and procedures.

5 Background

5.1 Rationale for Project

Alcohol Use Disorders (AUD's) are leading causes of disability in the United States. At present, three medications are approved by the FDA for the treatment of alcohol dependence: disulfiram, naltrexone, and acamprosate. However, the efficacy of these agents is minimal to modest, and they are under-utilized in clinical community settings (Garbutt et al 1999, Krishnan-Sarin et al 2008).

There is a pressing need for novel medications that are more effective in reducing alcohol use. Development of new pharmaco-therapeutic approaches to treating AUDs should emerge from our understanding of the behavioral and neurochemical mechanisms mediating pathological alcohol drinking. The goal of our center (the Center for Translational Neuroscience on Alcoholism; CTNA) is to evaluate the mechanisms through which disturbances in glutamate neurotransmission within cortico-limbic circuitry contribute to vulnerability for persistent heavy drinking, and to use this information to develop new therapies for alcoholism. In previous iterations of our center we have focused on evaluating if modulation of fast synaptic transmission via altering the ionotropic NMDA receptor function alters drinking behavior; our results suggest that the NMDA receptor antagonist memantine reduced craving for alcohol but did not influence drinking. In the current study, we would like to extend this work to examine the influence of metabotropic glutamate receptors which produce slower modulation of the glutamate system through second messenger systems.

5.1.1 Preclinical – Why examine the influence of an mGluR5 modulator on alcohol responses?

Our focus is mGluR5 receptors which have been shown to reduce intravenous drug selfadministration and reinstatement of drug-seeking in pre-clinical studies (Duncan and Lawrence 2012; Kenny and Markou 2004). mGluR5s are highly concentrated in nuclei associated with reward pathways such as the forebrain and limbic structures, dorsal striatum, Nacc, lateral septum, hippocampus, and cerebral cortex (Shigemoto et al., 1993, Romano et al., 1995). These receptors have also been shown to be involved in regulating motivation to self-administer alcohol (Hodge et al., 2006; Cowen et al., 2005; Besheer et al., 2008) as well as binge alcohol consumption (Tanchuck et al., 2011), mGluR5-deficient mice voluntarily consume less ethanol, are more sensitive to the hypnotic effects of ethanol (Bird et al., 2008, Downing et al., 2010), and display conditioned place preference to low doses of ethanol (1 g/kg) which suggests that they might have increased sensitivity to ethanol's centrally mediated rewarding affects. Moreover, in alcohol-preferring rats, administration of the mGluR5 antagonist MPEP Into the Nucleus accumbens reduces ethanol selfadministration; an effect which is not observed when MPEP is infused into the dorsomedial caudate or medial prefrontal cortex (Besheer et al., 2010). Moreover, human genetic studies have suggested that individuals with genetic variations in mGluR5, and the NMDA NR2A receptor subunits, have higher risk of developing alcohol dependence (Schumann et al., 2008). All the above evidence suggests there might be a role of mGluR5 receptors in alcohol reward/consumption.

5.1.2 Clinical Experience with Mavoglurant

Mavoglurant (AFQ056) is an experimental drug, developed by Novartis, which is a non-competitive antagonist of the metabotropic glutamate receptor subtype 5 (mGLUR5). Mavoglurant was developed to treat the behavioral and cognitive symptoms of fragile X syndrome (FXS). Pre-clinical data looked promising (Levenga et al., 2011), but clinical trials with FXS have found mixed results (Gomez-Mancilla et al., 2014; Petrov et al., 2014; Scharf et al., 2014). Mavoglurant has also been studied in pre-clinical (Morin et al., 2010; Grégoire et al., 2011) and clinical trials (Berg et al., 2011; Stocchi et al, 2013) for L-DOPA-induced

APPROVED BY THE YALE UNIVERSITY IRB 11/22/2023

2000021703 Version 2.9

dyskinesia (LID) in patients treated for Parkinson's Disease. Although results looked promising with antidyskinetic effects of LID, there was also inconclusive data (Kumar et al., 2013). Mavoglurant has also been studied in reducing chorea in Huntington Disease (Reilmann et al., 2015), and although the drug was well tolerated, the results did not suggest efficacy. Safety and tolerability of mavoglurant was established in a single dose trial in healthy male volunteers (Walles et al., 2013) and a clinical trial in patients with obsessive compulsive disorder (Rutrick et al., 2017), although the latter did not show efficacy. Although a clinical study was initiated in 2007 to assess mavoglurant on cigarette smoking, the results have not been published. To date, no trials have been conducted on the use of mavoglurant for alcohol use disorder (AUD).

Mavoglurant or AFQ056 is a structurally novel, subtype-selective, non-competitive antagonist at the metabotropic glutamate receptor 5 (mGluR5). We propose to use a dose of 200 mg because according to a receptor occupancy study conducted by Novartis this dose occupies about 90% of the mGluR5 receptors. The MTD of an immediate-release formulation of AFQ056 was observed to be 400 mg after single dose administration and 150 mg b.i.d. after multiple dose administration in healthy subjects. We will use a modified release formulation which has been shown to produce less fluctuation in C-max (80-90%) compared to an immediate release formulation.

6 Purpose, Risks, and Benefits

6.1 Purpose of Study/Potential Impact

The purpose of this study is to evaluate the safety and tolerability of a moderate dose of alcohol in combination with a non-competitive antagonist of the metabotropic glutamate receptor subtype 5 (mGLUR5), mavoglurant, on pharmacokinetic, physiological or behavioral responses in healthy social drinkers.

Prior to initiating a study to examine the influence of mavoglurant on drinking behaviors in heavy drinkers, we propose to conduct this study to examine the safety and pharmacokinetic interactions of administering mavoglurant and alcohol together.

6.1.1 Potential Risks

The major potential risks in this study are related to administration of alcohol, mavoglurant, and blood drawing during the physical exam and alcohol drinking period.

Risks Associated with Study Drug, Mavoglurant:

Mavoglurant of AFQ056 has been studied in a total of 2209 study subjects who have been enrolled in a total of 45 completed human studies, of which 29 were Phase I studies [single-dose: n=19; multiple-dose: n=10) and 16 were Phase II studies (eight studies in Parkinson's (PD-LID) patients, five studies in Fragile X (FXS) patients, one study in HD patients, one study in patients with GERD and one study in patients with OCD]. In these studies, a total of 1863 study subjects were exposed to AFQ056 while the remaining subjects received either placebo or an active comparator. The list of studies is included in Table 5.1 on page 47 of the investigator's brochure.

The maximum tolerated dose (MTD) of AFQ056 is 400 mg after single dose administration and 150 mg bid. after multiple dose administration (determined with immediate release-clinical service form (IR-CSF) in healthy subjects). Dose-limiting aEs were mainly hallucinations and other psychosis-like symptoms (e.g. paranoid reaction, anxiety, agitation, confusion, chaotic thoughts, disorientation in time/place, and mood changes).

Overall, the aEs observed in the various human studies were of mild to moderate severity. In patients with Parkinson's disease, dizziness (11.1%) and visual hallucination (11.1%) were the most common aEs in the AFQ056 treatment group (Table 5-10). Dyskinesia (12.0%), akinesia (8.0%), fall (8.0%) and asthenia (8.0%) were the most common aEs in the placebo group. Other AE's were headache (8.3%), anxiety, back pain, confusional state, constipation, fall, decreased hemoglobin, insomnia, muscle spasms, nasopharyngitis (common cold), nausea, edema peripheral (swelling in legs), orthostatic hypotension, parkinsonian gait, vision blurred, and asthenia, all at 5.6%.

In Fragile X Syndrome (FXS) patients, dizziness, insomnia, and headache were the most frequently reported aEs on AFQ056. Dizziness was also the most commonly reported AE in Parkinson's Disease-L-dopa induced dyskinesia (PD-LID), however primarily with the IR formulation. Other frequent aEs in PD-LID patients were mostly reflecting psychiatric disorders such as hallucination and illusion. In particular, the dose of 200 mg b.i.d. MR formulation appeared not to be well-tolerated, but this was primarily observed in patients receiving concomitant amantadine and there were no new safety concerns identified. Therefore, some flexibility in dosing is warranted to allow reduction to 150 mg b.i.d. dose, which had an acceptable tolerability profile.

The safety of AFQ056 in patients with moderate to severe OCD was assessed in a randomized, double-blind, placebo-controlled, single dose, in patients resistant to SSRI therapy (CAFQ056A2225; N=50). Patients in this study received AFQ056 200 mg BID upand down-titration regimen (4 weeks AFQ056 BID up-titration period of 50 mg, 100 mg, 150 mg and 200 mg, followed by 12 weeks AFQ056 200 mg fixed dose and then a 3-week down

titration. This study was completed in 2015 and the results indicate that this dose of AFQ056 was safe and well tolerated. There were six SAEs in three patients during the study. Two SAEs (otitis media and 7th nerve paralysis) in one patient from AFQ056 group and four SAEs in two patients from placebo group. There were three aEs (worsening OCD, insomnia, and moderate anxiety) which led to discontinuation of the study drug. All the events were considered as unsuspected to the study drug by the investigators.

12-Oct- 2014, investigator notifications have been issued for 22 subjects in completed and ongoing studies, of whom 14 were PD-LID patients, seven were FXS patients, and one was a subject in a healthy volunteer study (Section 5.2.1.2 of Investigational Brochure). Overall the events listed suggest that the central nervous system (CNS) and psychiatric system organ class (SOCs) may be preferentially affected.

Alcohol may also cause nausea in high doses; however, nausea is not expected at the dose being used in this sample of healthy volunteers who will report prior experience of consuming alcohol levels similar to the quantity used in this study. Alcohol dosing will be calculated using published gender specific algorithms based on estimated body water determined from height, weight, and age and the amount of alcohol provided will raise their blood alcohol levels to 80 mg/dl which is the legal limit of intoxication to levels.

Another area of potential risk to subjects under the influence of alcohol involves their safety during the experimental procedures. Although impairment of gross motor coordination in these subjects may occur, all subjects will be under the supervision of the experimenters to prevent possible accidents such as falls. To ensure the safety of our subjects, they will be monitored until their BAC falls to below .02 or until 6pm. All participants will be provided with transportation to and from the lab sessions to ensure their saftey.

There is no data looking at the effects of alcohol with mavoglurant. However, this interaction is the purpose of this study and the amount of alcohol that will be given subjects is no more than the amount they may drink in a social environment.

Risks associated with urine collections:

Screening urine collections are performed primarily as safeguards to subjects and should add no risks other than those normally associated with these procedures. Subjects will have approximately 50cc of blood drawn at the PE appointment to determine liver and kidney functioning. We will draw approximately 70.5cc of blood during the first lab session and 85.5cc of blood at the second lab session for BALs and health profile and PK samples. The morning after lab session 2, 50cc's of blood is drawn. At the 1 week follow up 50cc will be drawn again for health profile. Therefore, the total amount of blood drawn during the study (306 ml) is well within the HIC guidelines of 450 cc within 8 research weeks, and the blood loss poses minimal risk in healthy subjects. We will advise subjects against donating blood for 6 weeks following study participation.

BLOOD DRAW	PE	DS1	DS2	Morning after	1 WEEK F/U
Chem Profile (safety labs) 50 cc/draw	х	Х	Х	Х	Х
BAL (total 11 vials/visit) 0.5 cc/draw (5.5/DS)		Х	Х	Х	
PK Assay		Х	Х		
15 cc/draw			(2)		

Risks associated with rating scales and questionnaires:

These are all noninvasive and should add no risk. The major disadvantages are the time taken to complete them or possible discomfort in answering certain items.

Risks Associated with Blood Drawing:

Drawing blood is a safe and standard medical procedure. Sometimes a bruise will occur at the puncture site and rarely a blood clot or infection will occur in the vein. Certain individuals may feel light-headed during venipuncture.

Risks Associated with Electrocardiograms (EKG/ECGs) at the physical exam:

There is no pain or discomfort during an EKG/ECG; however, removing the pads may cause some irritation to the skin.

Risks Associated with Intravenous Access:

Insertion of an intravenous catheter involves risk for hematoma at the site of the venous puncture. Very rarely, venous puncture can also result in a blood clot or infection.

6.1.2 Potential Benefits

Subjects will not benefit from participating in this study. Subjects may benefit by receiving, at no charge, a thorough screening and diagnostic evaluation, the results of which may be shared with them, and if they wish, with their physicians. This research will also benefit scientific knowledge and may lead to the development of a potential therapy for alcoholism.

7 Study Objectives

7.1 Primary Objective

The primary objective of this study is to evaluate the safety and tolerability of mavoglurant when used in combination with a moderate dose of alcohol in healthy social drinkers.

Specific Aim 1: To evaluate the effect of mavoglurant on blood chemistries, urine toxicology and physiological safety measures before and after alcohol administration.

7.2 Secondary Objectives (if applicable)

Specific Aim 2: To evaluate the interactions of alcohol and mavoglurant on blood alcohol levels and mavoglurant levels.

We collected and analyzed mavoglurant levels from the first 10 participants who completed this study. These results did not show any changes in mavoglurant levels after alcohol administration. We collected blood sample from the additional 14 participants who recently completed the study but at present we do not have the funding to complete these assays which are rather expensive and can only be conducted by one company in India. So we would like to not conduct these assays on the new samples but we would like to retain the deidentified samples and conduct the assays at a later date if and when funding becomes available

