8.2.1 Secondary Outcome Variables (if applicable)

The secondary outcomes are blood alcohol levels on mavoglurant compared to no drug, and drug levels of mavoglurant before and after alcohol administration.

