At 2pm, subjects will be given lunch and will be monitored for any remaining alcohol effects. BAC levels will be taken every 30 minutes until the level falls to less than .02 (about 4 hours). Participants will be allowed to leave when their BAC falls to below .02 or at 6pm, whichever comes first. All participants will be provided with transportation to and from lab session.

Outpatient Treatment

At the commencement of drinking session 1, participants will be sent home with the study medication for the full period. If their second lab session is not scheduled within the designated timeframe, the participant will come in for their first medication appointment and be sent home with their medication that day. They will take their medication daily (in person or on video chat – 10min) at approximately 10am. They will be observed taking the study medication, for 7-10 days (to achieve steady state levels). This will ensure compliance with medication and allow us to monitor side effects daily. The last dose of study medication will be at 8:15 on the morning of their Lab Session 2. Participants will be asked to abstain from alcohol during the outpatient medication period; our rationale for requiring this is because this is a study to examine alcohol-drug interactions and we want to study these interactions in a controlled laboratory session.

Lab Session 2

See appendix for detailed procedure sheet. Participants will arrive at the Hospital Research Unit (HRU), Church Street Research Unit (CSRU), or Masonicare at 8:15am. They will be instructed to take their last dose of study medication. We will collect BAC, urine toxicology, and provide them with breakfast. Following breakfast, they will complete study assessments/questionnaires. We will put an IV catheter in the participant's arm at 11:00am and we will draw the initial set of labs. At 12:00pm, participants will be given their first drink of 80-proof vodka with a non-carbonated mixer of their choice and will be instructed to drink it in 15 minutes. They will continue to receive successive doses of alcohol in 6 equal portions (every 15 minutes) over a 90-min period designed to raise their blood alcohol levels to 80 mg/dl. Safety labs will be drawn and blood samples will be collected at regular intervals (at baseline and every 15 minutes during the lab session and then hourly for the next 3 hours) to assess blood alcohol levels and to assess Mavoglurant levels. They will complete paper

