9.4 Statistical Method

9.4.1 Statistical Design

This study is exploratory in nature and seeks to determine effect sizes to be used in subsequent years, in the larger-scale studies, and to determine if alcohol and mavoglurant can be safety used together. Therefore, no formal power calculations have been performed. The design employed here, including the chosen sample size, are relatively standard in pilot studies (Galasko et al., 1997; Sinha, et al., 1999)

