9.5.2 Secondary Objectives Analyses

Drug plasma levels for mavoglurant will be compared before and after alcohol consumption.

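### The before/after mavoglurant comparison at Lab Session 2 mixes alcohol with time since dose, so the null reported in 7.2 should not be read as absence of an interaction

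*Combined protocol and SAP*

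**What the plan says.** Specific Aim 2 (7.2) concerns interactions of alcohol and mavoglurant on two quantities: blood alcohol and mavoglurant levels. For the second, the outcome in 8.2.1 is "drug levels of mavoglurant before and after alcohol administration", and the whole analysis in 9.5.2 is "Drug plasma levels for mavoglurant will be compared before and after alcohol consumption".

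The timing is in 9.3: "The last dose of study medication will be at 8:15 on the morning of their Lab Session 2". The IV goes into the participant's "arm at 11:00am and we will draw the initial set of labs". The first drink is at 12:00 and the six portions take 90 minutes. Dosing runs "for 7-10 days (to achieve steady state levels").

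Section 9.2.2 gives one mavoglurant draw at Session 1, before any drug, and two at Session 2: one after the final dose and one after drinking. Under 8.1 everyone receives alcohol at both sessions.

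Section 7.2 already reports a result for the first 10 completers: "These results did not show any changes in mavoglurant levels after alcohol administration". It gives no number on drug, estimate, interval or sample times. Samples from 14 further completers are stored, and their assays are deferred for lack of funds.

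**The concern.** In participants on drug, the sample that follows alcohol is always also the later sample after the dose. A before/after difference is therefore the alcohol effect plus whatever the concentration curve would have done anyway over those hours. A flat result could mean that neither moved, or that the two offset each other.

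This matters because 6.1 gives as the reason for running this study before one in heavy drinkers the need "to examine the safety and pharmacokinetic interactions of administering mavoglurant and alcohol together", and 9.4.1 says the study "seeks to determine effect sizes to be used in subsequent years". With the other assays deferred, the sentence in 7.2 may remain the only answer to the mavoglurant-level half of Aim 2, and a later reader could take it as clearance.

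**Working it through.** **1. Number of drug samples at Session 2.** Volumes in 6.1.1 are 50 cc safety labs, 11 × 0.5 = 5.5 cc blood alcohol and 15 cc per drug assay.
- Session 1: 50 + 5.5 + 15 = 70.5 cc, as stated.
- Session 2: 50 + 5.5 + 2 × 15 = 85.5 cc, as stated.

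The budget supports the two Session 2 draws in 9.2.2.

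**2. Hours since dose (9.3).**
- Pre-alcohol: 8:15 to 11:00 = 2.75 h. This is an inference: 9.3 places the initial labs at 11:00, while 9.2.2 says only that the first draw follows the final dose.
- After drinking: 12:00 + 90 min = 13:30, and 8:15 to 13:30 = 5.25 h at the earliest.
- A late case: 17:00, when the IV is removed on the readable appendix sheet, is 8.75 h. That sheet appears to be for Session 1, so applying it to Session 2 is an assumption.

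The second sample is thus 2.5 to 6 h later after the dose than the first.

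**3. Can the effects be separated?** Session 1 precedes drug, placebo participants have no drug level, and no on-drug session without alcohol is described. With columns for intercept, later time and alcohol, the on-drug samples give only the rows (1, 0, 0) and (1, 1, 1): rank 2 for three unknowns. More participants repeat the same rows. An on-drug, no-alcohol reference at the same times would add (1, 1, 0) and bring the rank to 3.

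**4. Possible size of the drift (illustration).** The documents give no half-life, absorption rate or concentration profile, so these are assumed. For one compartment with first-order absorption, each dose contributes in proportion to

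f(x) = ka/(ka − ke) × [exp(−ke·x) − exp(−ka·x)], ke = ln 2 / half-life,

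summed over the last dose and 6 to 9 earlier daily doses. The last interval is 22.25 h (about 10:00 to 8:15). Half-life runs from 6 to 24 h, with **no alcohol effect**. If the observed ratio is 1.00, the implied alcohol effect is 1 divided by the time-only ratio.

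| Absorption | Second draw | Time-only ratio to 2.75 h | Implied alcohol effect |
|---|---|---|---|
| ka 0.1–0.5/h | 5.25 h | 0.97–1.17 | 0.86–1.03 |
| ka 0.1–0.5/h | 8.75 h | 0.71–1.16 | 0.86–1.40 |
| ka up to 2.0/h | 5.25 h | down to 0.75 | up to 1.33 |
| ka up to 2.0/h | 8.75 h | down to 0.50 | up to 1.99 |

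(Reciprocals use unrounded ratios, for example 1/1.169 = 0.86 and 1/0.713 = 1.40.) The number of earlier doses does not change these figures to two decimals.

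**5. Sampling error, separately.** With 14 per arm (8.1), the number on drug among 10 of 28 is hypergeometric with mean 5; 3 to 7 has probability 0.95. The 95% interval around a geometric mean ratio of 1 is exp(± t × SD/√n). With n = 5 and t = 2.776:
- SD of the log ratio 0.2 (assumed): exp(± 0.248) = 0.78 to 1.28.
- SD 0.4 (assumed): exp(± 0.497) = 0.61 to 1.64.

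The ranges in step 4 are not confidence intervals and should not be multiplied into these.

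**The case against.** **Steady state and modified release limit the drift.** In part. Steady state makes successive dosing intervals alike; it does not make the level flat within one. Section 5.1.2 says the modified-release form fluctuates less than immediate release, not that it is flat. Several profiles in the illustration are nearly flat, so the bias may be small. The documents do not show which case applies.

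**Section 9.3 can be read as serial drug sampling.** On that reading every post-alcohol sample is still later after the dose than the pre-alcohol one, with no alcohol-free reference. Separation would rest on an assumed curve shape. The wording also conflicts with 9.2.2 and the blood budget.

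**The protocol does not claim absence of an interaction.** This stands. Section 7.2 reports levels in a paragraph about deferring assays, 9.5.2 sets no test or margin, and 9.4.1 calls the study exploratory without tying effect sizes to drug levels. The point limits what may be concluded later.

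**The result is not empty.** This also stands. A reader might infer that the comparison says nothing. If the ratio was near 1, then with 5 on drug and SD 0.4, sampling error alone would exclude a halving or doubling, and the slow-absorption drift does not reach that size. That is weak evidence against a large interaction, though 7.2 gives no ratio with which to confirm it.

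**It is half of one secondary aim in a pilot whose primary objective is safety.** Agreed, and the severity reflects it.

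**Conclusion.** The concern holds in this form: the comparison in 9.5.2 cannot separate a modest alcohol effect on mavoglurant level from change within the dosing interval, whatever the sample size. The sentence in 7.2 should not be read as absence of an interaction; at most it is weak evidence against a large one.

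The confounding follows from the protocol's own clock and sampling plan. Its size and direction cannot be found from the documents, and the figures above rest on assumed kinetics, an assumed SD and an unknown time for the second draw.

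A reader might infer that an interaction exists and was missed; nothing in the documents shows that. Nor can it be said that the drift matters only if absorption is fast, because a late second draw also gives sizeable drift under slow absorption. The lack of a readable Session 2 clock time for the second drug draw is not counted as an omission, since that sheet may not have survived text extraction.

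The blood-alcohol half of Aim 2 is unaffected. Severity: minor to moderate.

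**What to change.** 1. In 7.2 and 9.5.2, state that the post/pre-alcohol mavoglurant ratio is descriptive, is confounded with time since dose, and will not be reported as absence of an interaction.
2. At reporting, and without breaking the blind described in 9.1.4, replace the verbal null in 7.2 with the number on drug, the geometric mean ratio with its 95% interval, and the actual post-dose times of both draws. Compare the ratio with a no-alcohol profile of the same formulation at those times if one is available.
3. Reconcile 9.2.2 (two Session 2 drug samples) with 9.3 (which reads as serial sampling).

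The cost is a wording amendment: IRB approval before implementation (10.2), then notice to the sponsor and FDA (10.13). No new visits, draws or assays are needed. The trial gives up an unqualified statement that drug level did not change. The fix does not remove the confounding, and assaying the 14 stored samples would narrow the interval without removing it either.
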